1.6.3.1 General Information

Fatigue is the most common side effect observed with immune checkpoint inhibitors, with an estimated overall frequency around 20% percent for the anti-PD-1 and anti-PD-L1 agents. However, the most relevant toxicities in clinical practice associated with these agents are immune-related adverse events (irAE).

1.6.3.2 Dermatologic Toxicity

Skin toxicity is the most common irAE related to immune checkpoint inhibitors, and approximately 30-40% of patients treated with anti-PD-1 and anti-PD-L1 agents will develop dermatologic complications. This toxicity usually is the earliest irAE, with a median time to onset of 3.6 weeks after treatment initiation. Typical physical examination findings consist of a reticular and maculopapular erythematous rash on the trunk or extremities. Severe rashes such as Stevens-Johnson syndrome/toxic epidermal necrolysis have been also reported in rare cases.

1.6.3.3 Diarrhea

Diarrhea is a very common clinical AE in patients undergoing treatment with immune checkpoint inhibitors. The onset of this toxicity occurs later than dermatologic toxicity, approximately six weeks after treatment initiation. Diarrhea of any grade has been reported in approximately 14,4% of patients treated with these agents, although grade 3 and 4 immune-mediated colitis has been seen in only 1-2% of cases. Potential risk of gastrointestinal perforation should be taken into consideration on patients with immune-related colitis.

1.6.3.4 Hepatotoxicity

Elevations in serum levels of the hepatic enzymes, aspartate aminotransferase (AST) and alanine aminotransferase (ALT), have been observed with anti-PD-1 and anti-PD-L1 agents in less than 5% of patients with grade 3 and 4 events being extremely rare. Most episodes are asymptomatic laboratory abnormalities, but occasionally patients have an associated fever. Increases in total and direct bilirubin are exceptional, and usually occur in association with a prolonged period of AST and ALT elevations. The most frequent time of onset is around two or three months after initiation of treatment, although early or delayed events may also be seen.

1.6.3.5 Endocrinopathies

Inflammation of the pituitary, thyroid, or adrenal glands as a result of checkpoint blockade often presents with imprecise symptoms such as nausea, headache, fatigue, and vision changes. Although it has been difficult to establish the exact incidence of endocrinopathies associated with these compounds, clinically significant events are thought to occur in less than 5-10% of patients treated with anti-PD-1 and anti-PD-L1 agents. The most common endocrinopathies are hypophysitis and autoimmune thyroid disease, principally primary hypothyroidism secondary to a destructive thyroiditis. Hyperthyroidism associated with Graves disease and adrenal insufficiency has also been reported with these compounds.

1.6.3.6 Less Common irAEs

Other less common irAEs have been attributed to anti-PD-1 and anti-PD-L1 agents, including:

- Nephritis (renal insufficiency, granulomatous interstitial nephritis, and lupus membranous nephropathy).
- Respiratory complications (sarcoidosis, pneumonitis, and organizing inflammatory pneumonia).
- Eye disorders (episcleritis, conjunctivitis, uveitis, or ophthalmopathy associated with Graves' disease).
- Pancreatic alterations [asymptomatic elevated levels of serum amylase and lipase and type 1 diabetes mellitus (T1DM)].
- Neurologic syndromes (myasthenia gravis, Guillain-Barre syndrome, posterior reversible encephalopathy syndrome, aseptic meningitis, enteric neuropathy, and transverse myelitis).
- Hematologic disorders (red cell aplasia, neutropenia, and thrombocytopenia).

1.7 Rationale for Dose Selection of INCMGA00012 (retifanlimab)

INCMGA00012 (retifanlimab) will be administered at 500 mg Q4W. The selection of this dose was based on modeling of clinical PK data from the first-in-human monotherapy study, INCMGA 0012-101 (NCT03059823), in which 37 participants from dose escalation phase were treated at doses of 1 mg/kg every 2 weeks (Q2W), 3 mg/kg Q2W, 3 mg/kg Q4W, 10 mg/kg Q2W, and 10 mg/kg Q4W and clinical experience with flat dosing in the expansion cohorts of the same study. Simulations demonstrated that the median steady-state trough concentration of retifanlimab 500

mg Q4W and 375 mg Q3W was approximately 21.1 µg/mL, which is the median trough concentration for pembrolizumab 2 mg/kg Q3W (48).

These dose regimens were further supported by the linear PK of retifanlimab and the final population PK analysis from 506 participants in 5 studies where body weight was identified as a statistically significant covariate for V_c but not for CL. Lack of correlation between CL and body weight minimizes an advantage of weight-based dosing over flat dosing on PK variability, especially for total exposure, as body size was believed to be a major contributor to inter-individual PK variability for mAb therapies

Based on these observations, 500 mg Q4W was chosen as the dose regimen. Preliminary efficacy data demonstrate clinical activity of INCMGA00012 (retifanlimab) based on durable RECIST responses in multiple tumor types (45).

1.8 Study Rationale

Currently, patients with patients with PSqCCs presenting with advanced disease continue to present poor prognosis and OS of <1 year. Best supportive care remains an option for advanced in this setting and consideration of clinical trial is strongly recommended by the NCCN panel of experts.

The majority of primary PSqCC tumors express PD-L1. On the other hand, in a recent study it has been showed that PSqCC presents an identical genotype compared to other HPV-related SqCC tumors and very similar to squamous NSCLC. These data provide a rational basis for further investigation of anti-PD-1 and anti-PD-L1 immunotherapeutic in patients with advanced PSqCC. Of the patients who do respond, many can have long-term survival and therefore there is much interest in identifying these patients using prognostic and predictive biomarkers.

For HPV-related cancers, the role of HPV as molecular marker ICIs-based therapy is quite scarce and not conclusive and future clinical trials should include the HPV status in the evaluation of prognostic/predictive biomarkers.

Preliminary data with INCMGA00012 (retifanlimab) in ~200 patients have shown promising antitumor activity, resulting in response rates similar to those observed with other ICIs. However, no data are available so far with anti-PD-1 and anti-PD-L1 agents used in this tumor subtype. In order to determine if immunotherapy could benefit this population, this multicenter, open-label, phase II clinical trial will evaluate the efficacy and safety of the of anti-PD1 INCMGA00012 (retifanlimab) in patients with advanced PSqCC previously treated or not with chemotherapy. Unlike other currently ongoing studies, this trial will evaluate the activity of immunotherapy in a series of patients with advanced PSqCC regardless of their prior treatment and extension of the disease.

2 STUDY OBJECTIVES AND ENDPOINTS

2.1 Primary Objective

- To assess the efficacy –as determined by the objective response rate (ORR)– of INCMGA00012 (retifanlimab) in patients with unresectable locally advanced or metastatic PSqCC.

2.1.1 Primary Endpoint

- ORR will be evaluated according to the investigator as per RECIST v.1.1.

2.2 Secondary Objectives

- To assess the efficacy –as determined by the clinical benefit rate (CBR), PFS, 6-month PFS, duration of response (DoR), time to progression (TTP), OS, and maximum tumor shrinkage– of INCMGA00012 (retifanlimab) in these patients.
- To evaluate the safety and tolerability of INCMGA00012 (retifanlimab) in these patients.

2.2.1 Secondary Endpoints

- OS, and clinical benefit rate (CBR), PFS, 6-month PFS, DoR, TTP, and maximum tumor shrinkage that will be evaluated as per RECIST v.1.1.
- The safety and tolerability will be evaluated by incidence of AEs, incidence of prespecified AEs, change from baseline in targeted vital signs, and change from baseline in targeted clinical laboratory test results.

2.3 Exploratory Objectives

- To determine the efficacy –as determined by the ORR, CBR, and 6-month PFS based on immune-related RECIST (irRECIST).
- To evaluate predictive or prognostic, tumor- and/or immune-related biomarkers associated with disease activity status or response to treatment.
- To identify possible mechanisms of resistance to study treatments through the comparative analysis of potential biomarkers from paired pre-treatment and post-progression tumor and/or blood samples.

- To assess impact of INCMGA00012 (retifanlimab) on HIV control in participants who are known to be HIV-positive.

2.3.1 Exploratory Endpoints

- ORR, CBR, and 6-month PFS as per irRECIST.
- Relationship between tumor- and/or immune-related biomarkers, and efficacy in tumor tissue and/or liquid biopsy.
- Changes from baseline in the CD4-positive cell count and HIV viral load in participants who are known to be HIV-positive.

3 STUDY DESIGN

3.1 Description of Study Design

This is a multicenter, open-label, single-arm, phase II clinical trial to evaluate the efficacy and safety of the INCMGA00012 (retifanlimab) in progressive advanced PSqCC patients, previously treated or not with chemotherapy.

The study population consists of male patients age ≥ 18 years with advanced PSqCC that are presenting with progressive disease. Patients that have received prior treatment of locally recurrent and/or metastatic disease with platinum-based chemotherapy regimens are not excluded.

In the absence of progression of disease or unacceptable toxicity, treatment with INCMGA00012 (retifanlimab) will continue based on physician's criteria for up to 2 years.

Tumor assessments per RECIST v.1.1 and irRECIST will be performed approximately every eight weeks (± 7 days) for the first 6 months and every 12 weeks (± 7 days) thereafter until PD, treatment discontinuation, the start of new anti-cancer treatment, withdrawal of consent, death, or the end of study (EoS), whichever occurs first. Tumor assessments will be performed on the specified schedule regardless of treatment delays.

For estimation of ORR, CBR, DoR, and PFS tumor response will be based on RECIST v.1.1. In patients who continue treatment beyond radiographic PD per RECIST v.1.1, tumor response (ORR, CBR, and PFS) may continue to be assessed using irRECIST criteria until study treatment discontinuation.

Safety assessments will include the incidence, nature, and severity of AEs and laboratory abnormalities graded per the NCI-CTCAE v.5.0. Laboratory safety assessments will include the regular monitoring of hematology, blood chemistry, coagulation, and thyroid function testing. A schedule of assessments is provided in **Appendix 1**.

3.2 Study Schedule Summary

The study will consist of a 28-day screening phase, a treatment phase, and a post-treatment phase (end of treatment [EoT] visit and EoS) that includes safety, efficacy, and survival follow-up.

3.2.1 Screening Phase

During this phase, subject eligibility is determined, including the documentation of baseline characteristics. This phase of the study will begin once the informed consent from (ICF) is signed by the patient and the procedures to be performed are described in **Section 6** of the protocol.

One re-screening is allowed in patients that are screening failure in this study. Patient has to re-consent the ICF before any study procedure is done.

3.2.2 Treatment Phase

Patients will receive study treatment according to the protocol and will be discontinued if one of the following situations arises:

- AEs which, according to the protocol or in the opinion of the Investigator, can cause serious or permanent damage or which rule out further treatment with the study drug.
- Progression of disease is confirmed radiologically and unequivocally assessed according to the RECIST criteria version 1.1 and/or irRECIST.
- Major study protocol non-compliance.
- Patient's withdrawal from the study.
- Death.
- Study is cancelled by the Sponsor.

3.2.3 End of Treatment Visit

EoT visit will be 28 days (± 7 days) after the last dose of study treatment.

3.2.4 Follow-up after treatment discontinuation

EoS will occur 12 months after the last patient has been enrolled in the study (treatment start).

Patients discontinuing the study treatment period will enter a post-treatment follow-up period during which survival and new anti-cancer therapy information will be collected every 3 months (\pm 14 days) from the last dose of investigational product until the end of study (EoS).

During this visit, status survival and post study anti-cancer therapy evaluation will be collected (telephone contact is acceptable).

LPLV: 12 months after first study dose of the last patient or progressive disease experienced in all patients or when the trial is terminated by the Sponsor, whichever is earlier.

4 PATIENT SELECTION

The following eligibility criteria can be used in the screening of patients for whom the protocol treatment is deemed suitable. In order to determine whether this protocol is suitable for a given patient, all medical and non-medical criteria should be taken into consideration.

Patient eligibility will be reviewed and documented by a suitable member of the Investigator's study team before the patients are enrolled in the study.

4.1 Study Population

Male patients age \geq 18 years with progressive locally advanced –not amenable to curative treatment– or metastatic PSqCC (i.e., T4 or N3 or M1) previously treated with chemotherapy regimens or patients naïve of systemic treatment.

The patient's signed ICF should be obtained before any trial related activities and according to local guidelines.

4.2 Inclusion Criteria

Patients must meet ALL the following inclusion criteria to be enrolled in the study:

1. Patients have been informed about the nature of study, and have agreed to participate in the study, and signed the informed consent form (ICF) prior to participation in any study-related activities.
2. Male patients \geq 18 years of age at the time of signing ICF.
3. Eastern Cooperative Oncology Group (ECOG) Performance Status (PS) 0-1.
4. Life expectancy \geq 12 weeks.
5. Histologically-proven PSqCC.

6. Locally advanced unresectable or metastatic stage 4 PSqCC that is not amenable to resection with curative intent (T4 or N3 or M1).
7. Radiological evidence of locally advanced or metastatic disease.
8. Patients must have measurable disease or evaluable disease according to Response Evaluation Criteria in Solid Tumors (RECIST) version (v.)1.1 criteria.
9. Patients must agree to provide a tumor tissue sample from a metastatic site or the primary tumor at the time of study entry, with the exception of patients for whom tumor biopsies cannot be obtained (e.g., inaccessible tumor or subject safety concern) that may submit an archived tumor specimen only upon agreement from the Sponsor. If feasible, patients will also be given the option of providing a tumor tissue sample at disease progression from metastasis or primary tumor (if tumor biopsies cannot be obtained for inaccessible lesion or subject safety concern).
10. Willingness and ability to provide blood samples (liquid biopsy) at the time of inclusion, after 2 cycles of study treatment (C3D1), and upon PD or study termination.
11. Adequate organ function:
 - Hematological: White blood cell (WBC) count $> 3.0 \times 10^9/L$, absolute neutrophil count (ANC) $\geq 1.5 \times 10^9/L$, platelet count $\geq 75.0 \times 10^9/L$, and hemoglobin > 9.0 g/dL.
 - Hepatic: Bilirubin ≤ 1.5 times the upper limit of normal (\times ULN) ($< 3 \times$ ULN in the case of Gilbert's disease); aspartate transaminase (AST), and alanine transaminase (ALT) ≤ 2.5 times \times ULN (in the case of liver metastases $\leq 5 \times$ ULN); Albumin > 2.5 mg/mL.
 - Renal: Serum creatinine $\leq 1.5 \times$ ULN; alternately measured or calculated creatinine clearance ≥ 30 mL/min with creatinine levels $> 1.5 \times$ institutional ULN (glomerular filtration rate [GFR] can also be used in place of creatinine or creatinine clearance).

 CL_{Cr} (mL/min) = (*Cockcroft-Gault equation: ($\{140 - \text{age in years}\} \times \{\text{ACTUAL WEIGHT in kg}\}$) divided by $\{72 \times \text{serum creatinine in mg/dL}\}$ multiplied by 0.85 if female)).

 $eGFR = 175 \times (S_{Cr})^{-1.154} \times (\text{age})^{-0.203} \times 0.742$ [if female] $\times 1.212$ [if Black]. From MDRD (49)
- Coagulation: Activated Partial Thromboplastin Time (aPTT) $\leq 1.5 \times$ ULN and International Normalized Ratio (INR) or Prothrombin Time (PT) $\leq 1.5 \times$ ULN unless subject is receiving anticoagulant therapy as long as PT or PTT is within therapeutic range of intended use of anticoagulants.
12. Patients who are willing and able to comply with scheduled visits, treatment plan, laboratory tests, and other study procedures.
13. Subjects should agree to use an adequate method of contraception starting with the first dose of study therapy through 180 days after the last dose of study treatment.

14. Patients that have received prior chemotherapy regimens or radiotherapy for locally recurrent and/or metastatic disease are not excluded but patients naïve of systemic treatment can also be included.
15. For pretreated patients, last dose of chemotherapy administered \geq 28 days from study entry.

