6.5 Safety and Tolerability Assessments

6.5.1 Laboratory Assessments

Laboratory tests will be performed in accordance to local standard treatment and clinical indications. These values will include:

- Hematological test [hemoglobin, hematocrit, red blood cell count, platelet count, WBC with differential count (ANC, lymphocytes, monocytes, eosinophils and basophiles)], coagulation, chemistry with renal function analysis (serum creatinine or measured/calculated creatinine clearance or GFR), liver function [AST, ALT, alkaline phosphatase (ALP), gamma-glutamyl transferase (GGT), total and direct bilirubin], glucose, sodium, potassium, calcium, chloride, magnesium, uric acid, total protein, albumin, and lactate dehydrogenase.
- Urinalysis (specific gravity, pH, glucose, protein, ketones, and blood).
- Thyroid function testing [thyroid-stimulating hormone (TSH), free T3, and free T4].
- HAV serology (positivity for HAV IgM antibody).
- HIV serology.
- HBV serology [HBsAg, anti-HBsAg].
- HCV serology (anti-HCV). In patients with a positive anti-HCV, HCV RNA detection and quantification by PCR will be additionally performed.
- Mantoux or Quantiferon tuberculin skin test (TST)

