8.3 Analysis Sets

Full analysis and safety set.

The full analysis and safety set includes patients who receive at least one dose of study medication.

Per-protocol set

All patients that accomplish selection criteria, receive at least one drug exposure, and receive the protocol required study drug exposure and processing. Criteria for determining the “per protocol” (PP) group assignment would be established by the Steering Committee before the statistical analysis begins. This analysis will only occur if this set differs by $\geq 10\%$ from the full analysis set.

Exploratory analysis set

All patients with biomarker evaluable samples with the assay and alternative platforms that accomplish selection criteria and receive at least one drug exposure.

Analysis set schedule

Primary, secondary and irRECIST endpoints will be analyzed on the full analysis set, and per-protocol populations. Full analysis set will be considered the primary population for the analysis. Biomarker and correlation between biomarkers and clinical outcomes will be analyzed on exploratory analysis set. Safety analysis will be performed on the safety set.

The estimands for the study based on ICH E9 (R1) addendum will be fully described in the statistical analysis plan.

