4 ANALYSIS SETS

The following sets will be analyzed:

- **Screening:** Patients who were present at the screening visit.
- **Safety and FAS (Full Analysis Set) Set:** patients who receive at least one dose of study medication.

Efficacy and Safety endpoints will be analyzed on the Safety/FAS set.

FAS set will be considered the primary population for the analysis.

- **Per-protocol (PP) set:** All patients that accomplish selection criteria, receive at least one drug exposure, and receive the protocol required study drug exposure and processing. Criteria for determining the “per protocol” (PP) group assignment would be established by the Steering Committee before the statistical analysis begins. This analysis will only occur if this set differs by $\geq 10\%$ from the FAS set.

The primary and secondary efficacy analyses will be performed on the FAS and PP sets.

- **Exploratory Set:** All patients with biomarker evaluable samples with the assay and alternative platforms that accomplish selection criteria and receive at least one drug exposure.

Exploratory analysis will be performed on exploratory set. A separate analysis report for such assessments will be written.

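### The albumin inclusion limit is written as 2.5 mg/mL (2.5 g/L), so low that it screens out no realistic patient

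*Protocol*

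**What the plan says.** The hepatic item of inclusion criterion 11 (Protocol Section 4.2) sets limits for bilirubin, AST and ALT, and then requires "Albumin > 2.5 mg/mL". Item 11b of the synopsis gives the same number and unit. The criterion is binding: "Patients must meet ALL the following inclusion criteria to be enrolled in the study".

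No other text supplies a different albumin limit or unit. Protocol Section 6.5.1 lists albumin in the chemistry panel ("uric acid, total protein, albumin, and lactate dehydrogenase") without a unit. The hematology/chemistry footnotes to Protocol Appendix 1 and SAP Section 1.5 do the same. The re-treatment criteria in Protocol Section 5.3 do not mention albumin, and the SAP sets no albumin limit.

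Two analysis sets refer back to eligibility. The per-protocol set (Protocol Section 8.3) is defined as "All patients that accomplish selection criteria, receive at least one drug exposure", together with the required study drug exposure. The exploratory set (SAP Section 4) takes patients with evaluable biomarker samples "that accomplish selection criteria and receive at least one drug exposure". On the per-protocol analysis, Section 8.3 adds: "This analysis will only occur if this set differs by" at least 10% from the full analysis set.

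**The concern.** A limit of 2.5 mg/mL lies far below any albumin concentration one would expect in a patient fit enough to be considered for this trial. It is the only albumin limit in the protocol, so if it screens nobody there is no albumin check at entry.

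Two things are at stake. The first is patient selection. A site that follows the text would enroll a severely hypoalbuminemic patient with no protocol deviation, while a site that assumes g/dL would turn the same patient away. The documents do not show that either has happened. The second is the secondary analysis sets. Both the per-protocol and the exploratory set depend on whether a patient met the selection criteria, and for some patients the answer depends on which unit is applied.

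**Working it through.** **Inputs from the documents**
- Written limit: more than 2.5 mg/mL (Protocol synopsis, item 11b; Section 4.2, criterion 11, hepatic).
- Neighboring unit: "hemoglobin > 9.0 g/dL" in the hematological item of the same criterion. The Cockcroft-Gault formula in Section 4.2 also uses serum creatinine per deciliter.
- Planned enrollment 18, with 16 evaluable (Protocol Sections 8.1 and 8.2).
- Per-protocol trigger: a difference of at least 10% from the full analysis set (Protocol Section 8.3; SAP Section 4).

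**Assumption.** The documents give no albumin range. I take 10 to 50 g/L, from severe hypoalbuminemia to the upper end of normal.

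**Step 1: convert the written limit.** 1 mg/mL = 1 g/L = 0.1 g/dL, so 2.5 mg/mL = 2.5 g/L = 0.25 g/dL.

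**Step 2: compare it with the assumed range.** 10 / 2.5 = 4 and 50 / 2.5 = 20. Every value in the range is 4 to 20 times the limit, so the item excludes none of them.

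**Step 3: convert the likely intended limit.** 2.5 g/dL = 25 g/L, and 25 / 2.5 = 10. Keeping the number and changing the unit to match hemoglobin raises the limit tenfold.

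| Albumin (g/L) | Passes > 2.5 mg/mL (as written) | Passes > 2.5 g/dL (likely intended) |
|---|---|---|
| 10 | yes | no |
| 15 | yes | no |
| 20 | yes | no |
| 25 | yes | no |
| 30 | yes | yes |
| 35 | yes | yes |
| 50 | yes | yes |

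The disputed range is above 2.5 and up to 25 g/L. Within the assumed range, that means 10 to 25 g/L.

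**Step 4: per-protocol trigger.** Suppose the stricter limit is used to decide who met the selection criteria, and there are no other per-protocol exclusions.
- 18 patients: 1/18 = 5.6%, below 10%, not run; 2/18 = 11.1%, run.
- 16 patients: 1/16 = 6.3%, not run; 2/16 = 12.5%, run.

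Either way, two patients in the disputed range would be enough. The documents do not say how many, if any, fall there.

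**The case against.** The unit is very probably a slip, but the case for treating it lightly has substance. The written limit is unambiguous: a patient with albumin of 20 g/L who was enrolled under this text did meet the selection criteria, and set membership changes only if someone later applies an unwritten limit. Protocol Section 8.3 and SAP Section 4 already leave the per-protocol criteria to the Steering Committee before analysis, so the unit does not decide membership mechanically. The two-patient figure is hypothetical: one unrelated exclusion would bring it down to one, and two would make it irrelevant. Per-protocol response rate is only a sensitivity analysis (SAP Section 5.4.2, Table 1), and the biomarker analyses run only if enough samples exist. Other entry limits remain active, including "alanine transaminase (ALT) ≤ 2.5 times" the upper limit of normal (relaxed for liver metastases), bilirubin, INR/PT, ECOG 0-1, life expectancy of at least 12 weeks and exclusion criterion 21. Finally, hemoglobin's unit does not prove what was intended for albumin.

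Most of this stands. It is fair that the error is one of eligibility wording rather than design calculation, that the effect on the analysis sets is conditional, and that the intended limit is inferred. None of it rescues the criterion, because none of the other limits is an albumin limit. If clinicians silently read g/dL, practice departs from the criterion against which eligibility is documented. The Steering Committee can settle set membership afterwards, but it cannot restore a check that was missing at enrollment.

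**Conclusion.** The concern holds. As written, the albumin sub-item of criterion 11 screens nobody across an assumed range of 10 to 50 g/L, where even the lowest value is 4 times the limit. The conversion is exact. The same unit in two places makes a fault in the PDF text unlikely, and nothing elsewhere corrects it. Only the albumin sub-item is inert.

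That the intended limit is 2.5 g/dL (25 g/L) is the most plausible reading, not an established fact. The consequences for the per-protocol and exploratory sets depend on patients actually falling in the disputed range and on which limit is later applied. The full analysis set (at least one dose), on which the primary analysis rests, does not depend on this item, and neither do the sample size, alpha, power or decision rule. The point deserves correction because it is a binding entry limit that bears on patient safety, not because it threatens the primary result.

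**What to change.** The sponsor confirms the intended albumin limit, most plausibly more than 2.5 g/dL (25 g/L), and corrects the unit in synopsis item 11b and in Section 4.2, criterion 11. The value itself is a clinical decision.

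If patients were enrolled under the written unit, the Steering Committee should record which limit applies when it sets the per-protocol criteria, before the analysis begins. The exploratory set should follow the same choice.

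The cost is one unit in two places. No statistical method or design figure changes.
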